Exclusion criteria: Individuals will be excluded based on a self-reported history of (1) unstable or significant current medical condition (recent heart attack or other heart conditions including high blood pressure); (2) severe immune system disorders (uncontrolled HIV/AIDS,

unstable multiple sclerosis symptoms), (3) respiratory diseases (exacerbations of asthma or COPD, require oxygen, require oral prednisone), kidney (dialysis) or liver diseases (cirrhosis) or any medical disorder/medication that may affect participant safety, study outcomes, or biomarker data will be excluded. Individuals who report more than 25 days of alcohol use in the past 30 days or more than 15 days of marijuana use in the past 30 days will be excluded. Individuals with past month use of cocaine, opioids, benzodiazepines, and methamphetamine will be excluded. Participants with current, diagnosed psychiatric conditions will also be excluded. Participants will be excluded for any use of an ENDS product in the past 30 days, or any report of daily use of ENDS for a week or more. Regular use of ENDS is excluded as we are interested in understanding the effect of these liquids on smokers who are relatively naïve to ENDS use so that prior experience does not obscure laboratory experience of use.

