- 1 Hr 05 min record Carbon Monoxide, 3rd set of questionnaire administration, *ad lib* use period begins (undirected use, participant can use as little or as much as they like)
- 2 Hr 35 min (*ad lib* period ends)
- 2 Hr 40 min Record Carbon Monoxide, 4th set of questionnaires
- 2 Hr 45 min Remove Catheter, Stop Physio Monitoring
- Payment
- Reminder of next appointment or thank participant for completion of study

Compensation: Participants will complete a W9 at their initial screening visit. Participants will receive \$75 after completing the first session, \$100 after completing the second session, and

\$125 after completing the third session (not counting the first lab visit for screening), resulting in a total payment of \$300. If a participant chooses to leave the study early, he or she will keep the amount earned up to that point. In addition, if a session must be discontinued for reasons beyond the control of the participant (e.g., difficulties with catheter insertion), the participant will be paid for the time spent complying with study conditions before the session began (\$15) and also the time spent in the laboratory (\$15/hour). The compensation amount of \$300 was chosen because of the number of hours that participants are asked to be in the laboratory (12.5 hours), which does not include the 12 hours that we ask them to abstain from tobacco products prior to each lab session (which can be very unpleasant for regular cigarette smokers). Thus, the compensation is felt to be appropriate.

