Risks to subjects: The protocol uses established methods and procedures and involves only minimal risks to participants. Twelve hours of tobacco abstinence may cause mild discomfort and nicotine abstinence symptoms, but is not medically dangerous. Symptoms may include: irritability, anxiety and restlessness, excessive hunger, difficulty concentrating, and sleep disturbance. The risks of using ENDS/tobacco products/nicotine are routine for the target population. As participation involves consumption of widely available, legal, over-the-counter products that can reduce the harm associated with their current nicotine use, they do not involve significant risks to participants. Risks of nicotine use by nicotine-naïve individuals include sweating, lightheadedness, dizziness, nausea, vomiting, and nervousness. These effects are unlikely in individuals who use nicotine-containing products regularly. In addition, some people who use e-cigarettes have reported experiencing seizures. Some of these individuals reported a prior history of seizures or using other substances at the same time as their e-cigarette. In many cases e-cigarette use has led to respiratory illnesses such as difficulties breathing, shortness of breath and/or chest pain before hospitalization. In some cases, e-cigarette use has led to death, and the Centers for Disease Control and Prevention has advised people to stop vaping. In some cases symptoms of mild to moderate gastrointestinal illness such as vomiting, diarrhea, or fevers or fatigue have been reported.

It is unlikely that the questionnaires will pose any potential risk or discomfort (no sensitive questions are asked). Sessions are relatively short and can be completed at the participants' own pace. With any research, there is always risk of loss of confidentiality. However, the risk is very low for the reasons listed below.

Steps taken to minimize risks / harms: Participant safety and rights will be protected by highly trained staff. Participants will be informed of the potential symptoms of nicotine abstinence/withdrawal and will be told they are free to leave the study at any time.

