An additional set of respiratory health questions will be administered by the nurse and/or RA to the participant at screening and then again prior to beginning each session. This will essentially minimize risk as these questions will serve as a supplementary screening tool which will help to determine whether the participant is in good health or ineligible for the study. These questions are included as an attachment (Additional Respiratory Questions). If 1 or more symptoms have increased since the participant's last visit, symptoms will be flagged for review by the medical monitor and will need to be reviewed prior to the participant's next session. If 3 or more symptoms have increased since the last visit, the medical monitor will need to be called in before the session can proceed.

In addition, non-invasive computerized monitoring equipment allows for minute-by-minute, real time monitoring of participants' heart rate (HR) and blood pressure (BP). Research personnel will be instructed to alert biorepository staff if HR exceeds 120 beats per minute, if systolic BP exceeds 150 mm Hg, or if diastolic BP exceeds 100 mm Hg. If HR and BP become elevated, research personnel will be instructed to alert the PI and the session will be stopped. The medical monitor will be available for consult during study sessions if needed. If systolic BP exceeds 180 or diastolic BP exceeds 120, 911 will be alerted. Emergency medical coverage is available across the street. Emergency medical care is available of the expense of the subject and/or their insurance. If systolic BP is between 150-179, diastolic is between 100-119, or HR is over 120, the subject will be monitored until these vital signs are reduced. If this does not occur within 1 hour, 911 will be called. These are anticipated to be very unlikely occurrences, as we exclude participants with resting HR above 110 BPM, systolic above 140, and diastolic above 100, and they are regular smokers in withdrawal consuming levels of nicotine that should be within or below their standard range.

In regards to nicotine abstinence symptoms, the products administered will likely alleviate these risks. Participants will be provided with water at all times.

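### No respiratory check follows the last product session, and one or two increased symptoms flagged at session 3 have no stated review point

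*Combined protocol and SAP*

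**What the plan says.** Steps taken to minimize risks / harms adds a set of respiratory health questions, given "at screening and then again prior to beginning each session". Two rules act on the answers, both triggered by symptoms that have increased since the previous visit:

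- One or more increased symptoms: they are "flagged for review by the medical monitor and will need to be reviewed prior to the" participant's next session.
- Three or more: "If 3 or more symptoms have increased since the last visit, the medical monitor will need to be called in before the session can proceed".

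The protocol schedules four laboratory visits: one for screening and three product sessions, with a different product at each. In the Experimental session timeline, ad lib use ends at 2 h 35 min and physiological monitoring stops at 2 h 45 min. The final entries are payment and "Reminder of next appointment or thank participant for completion of study". No later visit, call or questionnaire is described.

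Risks to subjects names the harm at issue: "In many cases e-cigarette use has led to respiratory illnesses such as difficulties breathing, shortness of breath and/or chest pain before hospitalization". The same section also says: "The risks of using ENDS/tobacco products/nicotine are routine for the target population". Exclusion criteria, however, states: "Participants will be excluded for any use of an ENDS product in the past 30 days". It also excludes anyone reporting daily ENDS use for a week or more, because the study wants smokers with little ENDS experience.

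**The concern.** The respiratory questions are the only instrument described in the protocol that could pick up respiratory symptoms arising after a participant has gone home. Because each administration comes before product use, an exposure is checked only if another session follows it. The last one has no successor.

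The review rule has a related weakness. For one or two increased symptoms, the deadline is set by a further session. Before session 3 none is to come, so the wording gives staff no point by which the monitor's review must be done.

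What is at stake is participant safety. A respiratory problem that begins after the final session would not be actively asked about, although the protocol itself names this kind of harm and adopts a tool for it. Describing ENDS risk as routine for these participants also fits poorly with recruiting people who are not recent or regular ENDS users.

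**Working it through.** The protocol states no figure to reproduce here, so the check sets the visit schedule against the two respiratory rules.

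**Inputs**

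- Question timing and both symptom rules: Steps taken to minimize risks / harms.
- Four visits, and 30 planned completers: Inclusion Criteria and Sample size.
- Three product sessions in a Latin-square order, each with a different product: Product consumption.
- End of session: Experimental session timeline.
- Sessions at least 48 hours apart: the section on the smoking/vaping lab sessions.

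**Step 1. Match each visit to the next check and the review deadline.**

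| Visit | Product used after the questions? | Next respiratory check | Deadline for a flag of one or two symptoms raised here |
|---|---|---|---|
| Screening | No | Session 1 | Not applicable |
| Session 1 | Yes | Session 2, at least 48 h later | Before session 2 |
| Session 2 | Yes | Session 3, at least 48 h later | Before session 3 |
| Session 3 | Yes | None | None: no further session |

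So 2 of 3 exposures are followed by a respiratory questionnaire. After the last one, monitoring continues for 10 minutes beyond the end of ad lib use (2 h 45 min minus 2 h 35 min).

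**Step 2. Count the sessions.**

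- Product sessions: 30 × 3 = 90.
- Last sessions: 30 × 1 = 30, and 30/90 = 33%.

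**Step 3. Split by product.** The protocol does not list the sequences. Assume each product comes last equally often, as it does in a 3-sequence cyclic square or in all 6 orders.

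- Each product is last for 30/3 = 10 participants.
- ENDS last: 2/3 × 30 = 20 participants.
- ENDS sessions in total: 30 × 2 = 60, so 20/60 = 33% have no later check.
- The other 10 unchecked sessions use the participant's own brand of cigarette, which is a usual exposure. The 20 of 60 is therefore the more relevant figure.

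**Step 4. Early leavers.** A participant who leaves after session 1 or 2 also has a last exposure with no later check. The number cannot be derived. The ceiling of 75 consents does not give it, because consent precedes the carbon monoxide, cotinine, pregnancy and vital-sign checks, and some of those consented may never use a product. Participants disqualified for failed abstinence are less clear, since they may have been asked the questions at the failed visit.

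**Step 5. Which session does the deadline mean?** The rule for three or more symptoms explicitly holds the session about to start. If the rule for one or more did the same, the two tiers would largely merge. The more natural reading is that one or two symptoms do not delay the current session and that review is due before the one after it.

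**The case against.** **The questions are a screening gate, not surveillance.** The protocol does call them a supplementary screening tool, and a gate has no role after the last exposure. But the trigger is an increase since the previous visit, and at sessions 2 and 3 that interval contains a product exposure. In practice the tool follows up two of the three exposures. This objection does not stand.

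**The deadline may refer to the session about to start.** Since the questions come just before a session, this is possible. The tiers would then differ only in that the monitor reviews in one case and is called in for the other, and session 3 would have a deadline. The wording for three or more symptoms makes this less likely but does not exclude it. So the second half of the point rests on the more probable reading of unclear text.

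**The answer may lie elsewhere.** The consent form and the attached respiratory form are not in the reviewed text and could carry reporting instructions. That stands as a limit: the point concerns the protocol's main text, which is where the timing and review rules are set.

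**Sessions are monitored.** Oxygen saturation, heart rate and blood pressure equipment and an available medical monitor cover the session itself. They do not cover symptoms that appear later.

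**Stronger readings that the documents do not support.** A reader might infer any of the following:

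- That symptoms flagged at session 3 are never reviewed. They are still flagged to the monitor; what is missing is a review point, and only for one or two symptoms.
- That ENDS is new to every participant. The exclusion covers use in the past 30 days and any history of daily use for a week or more, so earlier occasional use is allowed.
- That a tolerability conclusion is undermined. The research questions concern craving, withdrawal and appeal, and Data Analysis plans no tolerability claim.

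**Conclusion.** The point holds as a modest safety gap that is cheap to close. In the protocol text, the last product exposure has no later respiratory check: 30 of 90 product sessions with 30 completers, and 20 of 60 ENDS sessions if product order is balanced. Leavers after a product session add an unknown number. On the more natural reading of the review rule, one or two increased symptoms found before session 3 are flagged with no applicable deadline, while three or more are handled before that session proceeds. The first half follows directly from the schedule. The second depends on how the following session is understood. No planned comparison of craving, withdrawal, appeal, plasma nicotine or heart rate is affected.

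**What to change.** 1. In Steps taken to minimize risks / harms and in the session timeline, add one further administration of the existing Additional Respiratory Questions after each participant's last product session, including early leavers, by phone or REDCap link. The investigators and medical monitor should set the interval. The 48 hours between sessions is a scheduling figure, not a stated safety window, and should not be read as one.
2. Reconcile the review deadline with the three-session schedule so that a flag raised at session 3 has a review point, and say whether the deadline means the session about to start or the one after. The medical monitor sets the content and timing.
3. Reconcile the sentence in Risks to subjects that calls ENDS risk routine with the exclusion of recent or regular ENDS users.

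The cost is protocol wording plus one short contact per participant, using a form that already exists. Some participants will be hard to reach after final payment, so follow-up will not be complete.

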Laboratory space: Laboratory space in Williams Hall contains filtration devices to remove any secondhand smoke or aerosol (from cigarettes or ENDS). In consultation with [name] at Virginia Commonwealth University and [name], Executive Director of Facilities at EVMS, approximately \$50,000 was spent designing and equipping these rooms. This laboratory was designed for smoking research and includes a ventilation system so that others are not exposed to second-hand smoke unduly.

Sample size: A total of 30 participants are planned to allow for statistical power to examine differences (Within-Subjects) in the physiological and subjective effects of the products. Using a Repeated Measures Within-Subjects design, this will allow for detection of a large effect size (Cohen, 1992; Faul et al., 2009). We may consent up to 75 participants in order to obtain 30 participants who complete the entire study.

Recruitment: We will recruit current cigarette smokers using a recruitment database submitted separately (PR-2871-EVMS). Potential participants will find this recruitment database via advertising on Craigslist, newspapers, internet forums, flyers in the local area, and local clinics. There is a flyer specifically for this study that will direct individuals to participate in the registry online questionnaire. Screening data will be obtained from this online questionnaire. See separate protocol submitted. Screening data will be compared against the inclusion and exclusion criteria listed below to determine if participant is eligible for this study. Eligible participants will be contacted to provide more information about the study. Participants will be told they can smoke as normal for their first visit, but must abstain for 12 hours (typically overnight) before the 3 other visits. Those who meet screening criteria and are still interested in the study will be scheduled to come in for laboratory visits.

Inclusion Criteria: All participants must be healthy (determined by self-report), between the ages of 18-55, willing to provide informed consent, and willing to attend the EVMS lab 4 times and abstain from smoking for 12 hours (typically overnight) for 3 of these visits. Participants must smoke at least 10 cigarettes per day (i.e., be regular cigarette smokers). Self-report of smoking will be bioverified on the initial screening visit.

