
Smoking/Vaping" Lab Sessions: The sessions will occur no more than 2 days per week and will be separated by at least 48 hours. The approximate total time that participants will be in the laboratory is 12.5 hours (30 minutes for screening and 12 hours for 3 4-hour long sessions). This does not include the 12 hours before each session that we ask participants to abstain from smoking.

Note: Most questionnaires are completed via computer in the laboratory. The only exception for subjects is the glms, administered via pen & paper. EnrollmentInformation, SessionInformationSheet, BiochemicalTestResults, and the SaltStudySessionSheet are completed by Research Staff.

The session will begin with the participants' self-report of their last cigarette, CO expired air testing, and cotinine saliva testing. If the last cigarette smoked was within 12 hours or CO is above 10 ppm, the participant will be told they need to reschedule for another time and must abstain for 12 hours before the next visit. If there are 2 consecutive sessions indicating non-compliance, the participant will be disqualified from the study and paid as outlined in the compensation section. If participant's tobacco abstinence is bioverified, they will begin a 1-hour waiting period to ensure nicotine abstinence. Nicotine abstinence (e.g., ENDS, NRT) unfortunately cannot be bioverified quickly. Blood analyses at VCU CSTP have indicated high rates of lack of compliance, but much better data in protocols that involve a 1-hour waiting period in the lab. After this waiting period, the participant will continue on with physiological equipment attachment and catheter insertion. Physiological equipment (Criticare 506DNP3R, includes blood pressure cuff and SpOv2 sensor) will continuously measure BP/HR by trained Research Assistants or the study PI.

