The product that is used will be based on pre-established Latin-square order procedure (similar to random assignment) to avoid any order effects. For example, a participant may use the Subox Mini C with 18 mg regular (unprotonated) nicotine the first session, own brand cigarette the second session, and Subox Mini C with protonated nicotine on the last session. Participants will use a different product each session and use all 3 products by the completion of the study.

The cigarette will be purchased at a local retailer based on the participant's self-report in the baseline questionnaire of cigarette brand typically smoked. Smokers are often very loyal to a brand, so this will allow for a control condition of understanding standard reactions to cigarette smoking. The ENDS device will be a Subox Mini C, as recommended by VCU collaborators, who have had prior and current success using this device. The Subox will include a solution with either 18 milligrams/milliliter (mg/mL) of nicotine salt (protonated nicotine) or 18 mg/mL of regular (unprotonated) nicotine. The flavor will match their usual brand of cigarettes (tobacco-flavored or menthol-flavored).

Using a stopwatch, research assistants will instruct participants to take one puff of the tobacco product (cigarette or ENDS) every 30 seconds for 5 minutes. Participants will also complete another set of questions involving evaluation of the product consumed and nicotine withdrawal symptoms. Next, participants will be given 90 minutes to use *ad lib*, i.e., as much as desired. Smoking/vaping sessions will be videorecorded to allow for measurement of puff topography (puff duration, inter-puff interval, etc.). Final questionnaires will be completed. The participant will then be reminded of their schedule for the next session, if another session remains.

Experimental session timeline (approximate times):

- Participant arrives, CO test to confirm tobacco abstinence
- 1-hour waiting period (to help ensure nicotine abstinence), then the rest of the session will begin, as described below
- 0 Hr 0 min - Attach physio equipment, insert catheter, begin questionnaire administration
- 0 Hr 30 min - record Carbon Monoxide
- 0 Hr 35 min - 10 puffs from product (30s inter-puff interval)
- 0 Hr 45 min Record Carbon Monoxide, 2nd set of questionnaire administration

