used for each dependent variable. There are three within-subject tobacco products (own-brand cigarette, ENDS with unprotonated nicotine, ENDS with protonated nicotine) and four within-subject time points (pre-use, post-directed 10 puff session, pre-*ad lib* use session, post-*ad lib*). Three (condition) x four (time) repeated measures ANOVAs will assess plasma nicotine and heart rate (HR). Questionnaire items (or craving factors) will be examined individually using separate ANOVAs. Analyses conducted on the Hughes-Hatsuhashi Withdrawal scale, the Tiffany Drobis Questionnaire of Smoking Urges, and the Direct Effects of Nicotine (DEN) have 4 levels of time. The Direct Effects of E-cigarettes scale, unlike the DEN, only assesses reactions to the tobacco product and thus will have only 2 levels of time. Videorecordings will be evaluated via established methodology (Blank et al., 2009).

Any violations of sphericity will be adjusted using Huynh-Feldt corrections. In order to maintain statistical power and limit type 1 error for plasma nicotine, HR, and subjective effects, planned contrasts (paired samples *t*-tests) will be conducted across conditions at the two time points immediately after each use bout (e.g., each post-use session). At these two post-use timepoints, the mean value for each outcome measure in the protonated nicotine condition will be compared to the corresponding mean values in the unprotonated nicotine and cigarette conditions. Because these comparisons are non-orthogonal, a Bonferroni correction will be applied (Keppel, 1991).

References

CDC, 2011. Quitting smoking among adults--United States, 2001-2010. *MMWR Morb Mortal Wkly Rep* 60, 1513-1519.

Cohen, J., 1992. A power primer. *Psychological bulletin* 112, 155.

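### Product order is balanced by Latin square, but the planned ANOVAs and paired t-tests have no session-position term

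*Combined protocol and SAP*

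**What the plan says.** Product consumption sets each participant's sequence by a "pre-established Latin-square order procedure (similar to random assignment) to avoid any order effects". It does not list the orders, give their number, or say how people are assigned to them. One sequence is offered as an example: "regular (unprotonated) nicotine the first session, own brand cigarette the second session, and Subox Mini C with protonated nicotine on the last session".

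Under Data Analysis, "Three (condition) x four (time) repeated measures ANOVAs will assess plasma nicotine and heart rate (HR"; the four times are pre-use, after the directed puffs, before *ad lib* use and after it. Paired t-tests of protonated (salt) against unprotonated (regular) nicotine and against cigarette "will be conducted across conditions at the two time points immediately after each use bout", with a Bonferroni correction whose divisor is not given. No session, period or order term appears in any analysis, nor any check for one.

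Three other places matter:
- Sample size plans 30 completers and says "this will allow for detection of a large effect size". It also says "We may consent up to 75 participants in order to obtain 30 participants who complete the entire study".
- The lab-session section states: "If there are 2 consecutive sessions indicating non-compliance, the participant will be disqualified from the study". Compensation also provides for people who leave early.
- Exclusion criteria keep out regular ENDS users because the study wants people new to "ENDS use so that prior experience does not obscure laboratory experience of use".

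**The concern.** The design treats order as a threat and balances it, but the analysis then ignores the balanced factor. A drift common to all products does not vanish when orders are balanced. It cancels from the mean difference but stays in the spread of the paired differences, and so in the error term. If completers are not equal across orders, it does not cancel from the mean either, and part of it is read as a product effect. Nothing in the plan keeps completers balanced by order.

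A gain from first to second ENDS use is a different mechanism. It affects only the ENDS products, and whether it cancels depends on which orders are used. The protocol does not state them.

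**Working it through.** **Inputs.** From the documents: 30 completers, three products, three sessions, two planned comparisons at two post-use times. Assumed: SD of a paired difference = 1; linear drift g per session; gain L on second ENDS use; two-sided alpha 0.05/4 = 0.0125; dz=0.8 as a reading of *large*; dz=0.645 as the effect with 80% power. Both g and L may be zero.

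**1. The plan's own figure.** N=30 cannot be strictly reproduced, because alpha, power and the effect metric are not stated. It is compatible with a large effect: a paired t-test at dz=0.8 has power 0.988, 0.974 or 0.950 at alpha 0.05, 0.025 or 0.0125.

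**2. Drift, balanced orders.** The example belongs to the cyclic square regular-cigarette-salt, cigarette-salt-regular, salt-regular-cigarette. Salt position minus regular position is +2, -1, -1. The mean is 0 and the mean square is (4+1+1)/3 = 2, so drift adds nothing to the mean and 2g² to the observed variance. Six orders give the same: (4+4+1+1+1+1)/6 = 2. At g=0.5 the observed SD is √(1+0.5) = 1.22. The test then uses a standard error of about 1.22/√30 = 0.224, when the true one is 1/√30 = 0.183. Simulation (40,000 trials per cell, alpha 0.0125):

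| g | Type I error, paired t | Power, dz=0.8 | Power, dz=0.645 |
|---|---|---|---|
| 0 | 0.012 | 0.95 | 0.80 |
| 0.2 | 0.009 | 0.94 | 0.77 |
| 0.3 | 0.007 | 0.92 | 0.73 |
| 0.5 | 0.003 | 0.85 | 0.60 |

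With session position in the model, power is about 0.95 and 0.80 at every g.

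**3. Drift, unequal completers (three orders).** With a completers in the regular-first order, bias in salt-regular is g × [2a - (30 - a)]/30 = g × (3a - 30)/30. For a = 14, 9 or 7 this is +0.4g, -0.1g or -0.3g; salt-cigarette gives the same absolute values. At g=0.5 the largest is 0.4 × 0.5 = 0.20 SD. With session position the bias is zero.

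**4. Cost of the term.** Residual df fall from 29 to 27; with no drift, power at dz=0.645 goes from 0.801 to 0.797. With balanced orders the standard error stays at 0.183. At 14/9/7 it is (1/3) × √(1/14 + 1/9 + 1/7) = 0.190, about 4% more.

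**5. ENDS gain (secondary).** In the cyclic square, salt is the second ENDS in one order and regular in two.
- Salt-regular, three orders: shift (10 - 20)/30 × L = -L/3, or -0.17 at L=0.5, with or without session position. False positives are 0.031 for the paired t-test and 0.052 with the term.
- Salt-regular, six equal orders: (15 - 15)/30 × L = 0. False positives are 0.005 and 0.011.
- Salt-cigarette: 10/30 × L = L/3 with three orders, but 15/30 × L = L/2 with six. At L=0.5, with no difference at first ENDS use, the paired t-test rejects about 0.04 and 0.10 of the time.

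**6. Can a second-ENDS term be fitted?** Three orders give only three mean paired differences. Product and two session-position terms use all three, so a second-ENDS term cannot be added to the paired regression. Six orders can carry both.

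**The case against.** The Latin square already guards against order effects. Under balance, leaving out the term costs efficiency only: there is no bias, the tests err on the safe side, and at the large effect planned for power stays at 0.92 or more up to g=0.3. A common drift is also not the likeliest mechanism. The cigarette is the participant's own brand, sessions are at least 48 hours apart, and each starts with a smoking-abstinence check and a one-hour wait. The mechanism the text points to is ENDS learning, which session position does not remove. The example is only an example, and a pre-established procedure implies that a list exists somewhere.

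All of this stands as a limit on size. It does not remove the point, because balance among completers is not secured and the term costs almost nothing.

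Five stronger readings are tempting, and the documents do not support them:
- *The planned contrasts are biased.* Common-drift bias needs both a drift and unequal completers; neither is shown.
- *Three orders are used.* The example fits six orders equally well.
- *Recruiting 75 for 30 makes serious imbalance likely.* Consent comes before the CO, cotinine, pregnancy and vital-sign checks, so the 75 includes screen failures. A bias of 0.2g at g=0.3 is 0.06 SD, a third of the 0.183 standard error.
- *Salt against regular is the main question.* The research questions also name own-brand cigarette and rank neither comparison.
- *Six orders solve the learning problem.* They move more of it into salt-cigarette.

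**Conclusion.** The point holds in a limited form and is worth considering, with medium confidence. The analysis omits the factor that the design balances. With balanced orders, the consequence of a common drift is lost power: small at a large effect (0.95 to 0.92 at g=0.3, 0.85 at g=0.5) and larger near the 80% power point (0.80 to 0.73 or 0.60). With unequal orders there is also bias, up to 0.4g at 14/9/7. The sizes rest on assumed values of g, the completer split and alpha; the documents give none of these. The learning point depends further on which orders were used and on a gain existing. Its effect on salt-cigarette counts as bias only if the comparison is meant to describe first ENDS use.

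**What to change.** In Data Analysis:
- Estimate each planned contrast, separately at each post-use time, by regressing the within-participant paired difference on session position. Equivalently, fit product, session position and fixed participant effects to the two products compared.
- Add order as a between-participants factor, with its interactions, in the ANOVAs; order × product then carries session position.
- Report completers per order, and keep the plain paired t-tests as a sensitivity analysis.
- If a random participant effect is used to bring in incomplete participants, state that it matches the paired regression only when orders are balanced.

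In Product consumption, list the orders and how people are assigned to them. If all six are used equally (five completers each), state the trade: the salt-regular shift from an ENDS gain goes to zero, and the salt-cigarette shift rises from a third to a half of the gain.

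For either schedule, report both salt-regular and salt-cigarette with a second-ENDS-session term as a sensitivity analysis. With six orders it can sit beside session position. With only three it must either replace session position in the paired regression or come from one model over all three products. In that model the salt-regular standard error rises about 12% (0.183 to 0.204) and a common error variance is assumed.

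The main change costs SAP wording, 2 df per contrast and about 4% in standard error at 14/9/7. It needs no new data. The second-ENDS analysis is less precise for salt-cigarette: with six orders only 15 participants use salt as their first ENDS, so without session position the standard error is 1/√15 = 0.258 against 0.183. It should therefore stay a sensitivity analysis.
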